# 2.10. RESULTS

Through the research, the effectiveness or the ineffectiveness of the FM will be highlighted and comparisons will be made between the effect of FM and A-S, regarding specific parameters (outcome measures), that will be evaluated at specific times (before and after the completion of the intervention - five weeks). Findings will be drawn for each hypothesis of both research questions with the aim of verifying or rejecting them. In detail, pain sensitivity, cervical ROM, endurance of the deep neck flexor muscles, respiratory function, intensity and quality of pain, functionality and psychological factors will be assessed and contrasted between the two interventions. After comparing the mean values of the groups in each assessment for each outcome measure, it will be established on the first level if the method under consideration has benefits in patients with chronic neck pain. On the second level, it will be established if it shows statistically significant results compared to the A-S intervention, if non-significant differences are detected between the two groups or if the active control group predominates. The findings will be presented for each outcome measure separately.

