# 2.3. RESEARCH HYPOTHESISES

Two main research questions are formulated regarding the effectiveness of ATM versus a standard treatment regimen consisting of acupuncture and stretching, but also the effectiveness of ATM as monotherapy, which will be investigated through appropriate statistical controls. The formal basis of statistical tests is the null hypothesis under which there is no association between the exposure and the outcome (Killeen, 2005). Starting from the assumption of no relationship, statistical tests quantify the probability that the observed relationship was observed by chance, due to the random sampling distribution. When the null hypothesis cannot be rejected then the observed relationship is attributable to chance rather than a true effect of the exposure on the outcome (Banerjee *et al.*, 2009).

Thus, the null hypotheses to be tested are formulated as follows:

- Research question 1: Effectiveness of ATM (intervention group before the intervention vs. the same group after the intervention)
  - Null hypothesis H0A1: The application of ATM does not affect the pain sensitivity assessed by the Pain Pressure Threshold (PPT) measured

with the pressure algometer (Commander Algometer) in patients with chronic neck pain (main hypothesis).

- Null hypothesis H0A2: The application of ATM does not affect the cervical range of motion (ROM) recorded with the Moover threedimensional (3D) Inertial Motion sensor in patients with chronic neck pain (secondary hypothesis).
- Null hypothesis H0A3: The application of ATM does not affect the strength of deep neck flexor muscles as measured by the Chattanooga Stabilizer Pressure Biofeedback in patients with chronic pain in the cervical spine (secondary hypothesis).
- Null hypothesis H0A4: The application of ATM does not affect the respiratory function assessed by the portable spirometer (MIR Spirodoc) in patients with chronic neck pain (secondary hypothesis).
- Null hypothesis H0A5: The application of ATM does not affect the pain in the cervical spine in terms of its intensity and quality, i.e., its sensory, emotional and behavioral dimensions using the McGill Pain Questionnaire-short form (SFMPQ) in patients with chronic neck pain (secondary hypothesis).

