- Null hypothesis H0A6: The application of ATM does not affect the functionality recorded with the Neck Disability Index (NDI) in patients with chronic pain in the cervical spine (secondary hypothesis).
- Null hypothesis H0A7: The application of ATM does not affect the anxiety and depression captured by the Hospital Anxiety & Depression Scale (HADS) in patients with chronic neck pain (secondary hypothesis).
- Null hypothesis H0A8: The application of ATM does not affect the kinesiophobia as measured by the Tampa Scale Kinesiophobia (TSK\_GR) in patients with chronic neck pain (secondary hypothesis).
- Null hypothesis H0A9: The application of ATM does not affect the perception of the fear and the effort to avoid pain in relation to physical and work activities assessed by the Fear Avoidance Beliefs

Questionnaire\_Greek version (FABQ\_GR) in patients with chronic neck pain (secondary hypothesis).

- Null hypothesis H0A10: The application of ATM does not affect the degree of pain catastrophizing recorded by the Pain Catastrophizing Scale (PCS) in patients with chronic neck pain (secondary hypothesis).
- Null hypothesis H0A11: The application of ATM does not affect the quality of life as measured by the Short Form 12-item Health Survey (SF-12) in patients with chronic neck pain (secondary hypothesis).
- Research question 2: Effectiveness of ATM versus A-S
  - Null hypothesis H0B1: The effect of applying ATM does not differ in reducing the pain sensitivity (PPT) in patients with chronic neck pain from applying A-S (main hypothesis).
  - Null hypothesis H0B2: The effect of the application of ATM does not differ in the improvement of the cervical ROM in patients with chronic neck pain from the application of A-S (secondary hypothesis).
  - Null hypothesis H0B3: The effect of applying ATM does not differ in improving the strength of deep neck flexor muscles in patients with chronic neck pain than applying A-S (secondary hypothesis).
  - Null hypothesis H0B4: The effect of the application of ATM does not differ in the improvement of the respiratory function in patients with chronic neck pain from the application of A-S (secondary hypothesis).

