# 2.4. OBJECTIVE GOALS

Objectives of the study are summarized in the investigation of statistically significant differences in the outcomes of interest, i.e. in the measurements for pain sensitivity, intensity and quality (pressure algometer and SFMPQ), functionality (NDI), ROM (Moover 3D Inertial Motion sensor), endurance of deep neck flexor muscles (Chattanooga Stabilizer Pressure Biofeedback), respiratory function (portable spirometer) and psychological parameters (HADS, TSK, FABQ, PCS, SF-12). Differences in the outcomes of interest may arise:

a) between the start time (baseline) and the end time of the study within the A-ATM group (A-ATM group at baseline versus A-ATM group after the intervention).

b) between the compared groups of the clinical trial {group A ATM (Intervention Group) versus group B A-S (Active Control Group)}, both at the beginning of the study, as well as after the intervention.

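### Benefit of ATM can be concluded from an uncontrolled before-after change, and no PPT variable is designated for the randomised comparison

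*Combined protocol and SAP*

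**What the plan says.** Section 2.3 poses two research questions. The first is "Research question 1: Effectiveness of ATM (intervention group before the intervention vs. the same group after the intervention". Its PPT hypothesis, H0A1, concerns pain sensitivity measured "with the pressure algometer (Commander Algometer) in patients with chronic neck pain (main hypothesis". The second question is ATM against A-S, and its PPT hypothesis, H0B1, states that the effect of ATM "does not differ in reducing the pain sensitivity (PPT) in patients with chronic neck pain from applying A-S (main hypothesis". Two hypotheses on the same outcome are therefore both labelled main. Section 2.4(a) repeats the first as an objective: "A-ATM group at baseline versus A-ATM group after the intervention".

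Section 2.10 sets out how conclusions are reached. "Findings will be drawn for each hypothesis of both research questions with the aim of verifying or rejecting them". One sentence there opens with a loosely worded step, "After comparing the mean values of the groups in each assessment for each outcome measure", and goes on to the first-level conclusion: "it will be established on the first level if the method under consideration has benefits in patients with chronic neck pain". The next sentence turns to the active control: "On the second level, it will be established if it shows statistically significant results compared to the A-S intervention".

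On the outcome itself, section 2.5.3.1.1 describes PPT measurement at a list of body points and records, at each point, the mean of the second and third readings. Section 2.9 specifies a linear mixed model with group, measurement (endline against baseline) and their interaction, and a two-sided threshold of 0.05. It does not say which PPT value enters the model.

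**The concern.** A change from before to after in one treated arm mixes the effect of the treatment with everything else that happens over five weeks: natural course, regression to the mean, attention and expectation. A&#8209;S is an active treatment, so the trial has no arm that shows what would have happened without treatment. Section 2.5.1.2 adds a further problem. One assessor takes the baseline measurements and a second takes the final ones, so time point and assessor are completely confounded. The only algometer reliability quoted in section 2.5.3.1.1 is intra-rater. An assessor offset common to both arms cancels in the group-by-measurement interaction but stays in full in H0A1.

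If the plan is followed as written, the trial could report that ATM is beneficial because of a change patients might have shown anyway. No multiplicity correction cures that, because the error is bias and not chance.

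The second gap concerns H0B1 itself. With several PPT values per patient and none designated, sites that disagree leave the main randomised hypothesis without a defined answer.

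**Working it through.** **1. The plan's sample size, used here for the number per arm.** Section 2.5.1.1 gives 126 patients for effect size 0.25, 80% power and 5% significance. With a standardised difference d, n per arm = 2(1.960 + 0.842)²/d².
- With d = 0.5 (0.25 read as Cohen's f for two groups): 2 × 7.85/0.25 = 62.8, so 63 per arm and 126 in total. This reproduces the plan.
- With d = 0.25 (the formula printed in 2.5.1.1): 2 × 7.85/0.0625 = 251.2, so 252 per arm and 504 in total. This does not.

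That conflict is a separate matter. Here I take 63 per arm (half of 126) and 76 per arm (section 2.5.1.2).

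**2. The texts side by side.** Section 2.3 (question 1) and 2.4(a) make the before-after comparison a question about effectiveness. Section 2.10 promises a finding on every hypothesis of both questions, then names two levels. The second level is ATM against A-S. If the first were also ATM against A-S, the two would duplicate each other, so the first level is naturally question 1. Section 2.1 fits this reading: it states the aim of examining ATM as a single intervention separately from the comparison with A-S. The limitations in 2.11 do not mention the lack of an untreated control.

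**3. The within-arm test when ATM has no specific effect.** A paired t-test, two-sided 0.05, stands in for the within-arm contrast. The noncentrality is δ√n, where δ is the non-specific shift in SD of the change score (assumed).

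| δ (assumed) | n = 63: δ√n | Significant | n = 76: δ√n | Significant |
|---|---|---|---|---|
| 0.2 | 1.59 | 34.6% | 1.74 | 40.6% |
| 0.3 | 2.38 | 65.0% | 2.62 | 73.3% |
| 0.5 | 3.97 | 97.4% | 4.36 | 99.0% |

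**4. The randomised contrast in the same scenario.** With an equal shift in both arms and 63 per arm, 100,000 simulated trials gave a significant difference in change between groups in 5.1%, 5.1% and 5.0% of trials. That 5% depends on the shift being equal. If the arms differ in non-specific effect by 0.1 or 0.2 SD of change (assumed), the noncentrality is 0.1 × √(63/2) = 0.56 or 1.12, and the test rejects in 8.6% or 20.0% of trials. These are not false positives for H0B1, which compares whole packages (ATM in groups of 6-8, A-S in individual sessions). They show that H0B1 does not isolate attention either.

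**5. The PPT variable.** Section 2.5.3.1.1 names the upper trapezius, the mastoid process and BL 10 first. It then adds C5-C6, tibialis anterior, middle deltoid and levator scapulae. That makes 3 + 4 = 7, as a reading of an open-ended list with no body side fixed. Suppose, hypothetically, that a significant result at any one site could answer H0B1. With no true group difference and each site tested at 0.05, the chance of at least one significant site is 1 − 0.95^k for k independent sites. For correlated sites it comes from 400,000 equicorrelated normal draws.

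| Inter-site correlation (assumed) | First three points | All seven points |
|---|---|---|
| 0 (upper bound) | 14.3% | 30.2% |
| 0.5 | 12.5% | 22.9% |
| 0.8 | 9.8% | 14.8% |
| 0.9 | 8.3% | 11.4% |

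Simulated t-tests with 63 per arm (20,000 trials) agreed to within half a percentage point. If both body sides were measured and tested (14 tests, assumed), the figures would be 51% at correlation 0, 35% at 0.5 and 14% at 0.9. With one variable named in advance the chance is 5%.

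**The case against.** The sentence in 2.10 opens by speaking of comparing the groups, the sentence before it contrasts the two interventions, and 2.12 says the effect of ATM will be established by a randomised trial. On those words alone, the first level might be a group comparison. This stands as far as 2.10 by itself is concerned: the point rests on 2.3 and 2.4(a), which are explicit, together with the promise in 2.10 to decide every hypothesis of both questions.

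A before-after question is legitimate as description, and the plan states openly that it is one. That is true. What cannot be supported is calling it effectiveness, giving it main status and concluding benefit from it.

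The bias may be modest. Section 2.5.1.5 sets no minimum pain or PPT for entry and requires at least three months of symptoms, so patients are not selected on PPT. This weakens regression to the mean, although clinic attendance may still select flares. It does not touch attention, expectation or the change of assessor. The documents give no size for the shift, so section 3 of the working illustrates and does not estimate.

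The multi-site figures depend on a rule the plan never states, and treating the first three points as a core is an inference. Both remarks are right. The text shows only that no variable is designated and that the any-site reading is not ruled out.

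Finally, a single primary H0B1 exposes the power problem. Under the effect-size formula printed in 2.5.1.1, 63 per arm gives about 29% power. That is so, but it is true of H0B1 whether or not H0A1 keeps its label.

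**Conclusion.** Both parts hold, and the plan should be changed. The text lets an uncontrolled within-arm change in a main hypothesis support a claim of benefit that the design cannot bear. With no specific ATM effect, that test would be significant about 35% to 97% of the time with 63 patients and 41% to 99% with 76, for assumed shifts of 0.2 to 0.5 SD of change.

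For H0B1, no site, side or composite is designated at an unadjusted 0.05. Under the hypothetical any-site rule, the false-positive chance at assumed correlations of 0.9 to 0.5 is 8% to 12.5% for the first three points and 11% to 23% for all seven.

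The first part rests on reading 2.3, 2.4(a) and 2.10 together; the second rests on 2.5.3.1.1, 2.3 and 2.9. Neither depends on the illustrative figures. The randomised test, H0B1 by the group-by-measurement interaction, is sound in form. The defects are the status and interpretation given to research question 1, and the missing definition of the PPT variable.

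**What to change.** Make these changes, dated, before any outcome data are seen by group:

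- Make H0B1 at five weeks, tested by the group-by-measurement interaction already in 2.9, the single primary test.
- Name one PPT variable for it: either one site or one composite over neck sites, with the member sites and the body side listed. Report the remaining sites as secondary.
- Remove the main label from H0A1, and describe research question 1 and 2.4(a) as within-arm change. Reword 2.10 so that any conclusion of benefit rests on the randomised comparison and is stated relative to A-S.

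These are changes of wording in the protocol and SAP; they need no new patients, visits or measurements. Recruitment was to start on July 25, 2022, so if outcomes have already been seen by group, the choice of PPT variable must be reported as post hoc. Rewording the benefit claim is useful at any time. The price is that a before-after result or a single favourable site can no longer be presented as the primary finding. The effect-size conflict in 2.5.1.1 needs its own correction, since it determines the power of the test that remains.

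A separate, minor point enters none of the figures. Section 2.8 plans a four-month measurement that feeds the dropout rate but has no planned outcome analysis, while 2.5.3, 2.9 and 2.10 stop at five weeks and 2.11 says there will be no follow-up. These sections should be reconciled.

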## 2.11. DISCUSSION

In the discussion the results will be recapitulated, analyzed and related to the existing literature. Each studied parameter of each research question will be assessed separately and the correlation based on the results obtained from the existing literature, which will be listed in the general part, will be highlighted. If the hypothesis is verified, then it will be compatible with the findings of the studies so far. Otherwise, it is against them. Finally, the above will be interpreted and the reason will be justified.

The aim of each study is to minimize the limitations, in order to draw safer conclusions and then to generalize the results.

The sample will consist of a wide age and social spectrum, which provides more reliability to the study and increases the power of the FM, giving the possibility of its application without limitations. Furthermore, a wide variety of parameters will be evaluated in a large sample size, providing the possibility of deriving statistically significant results. The number of the participants is satisfactory and larger than that of the majority of studies analyzed in the literature review. Additionally, recording the compliance rate is an additional advantage and is not included in the most studies.

In the limitations is included the design of the study, which is a 'single-blind' method, eliminating systematic error for the observer. Another limitation is represented by the heterogeneity in the severity of the patients' symptoms, which could be specified in the inclusion criteria. Also, the plethora of exclusion criteria, that were set due to the acupuncture may constitutes an obstacle to the promotion of the results in the general population. Last but not least, short-term or long-term follow-up will not be conducted.

# 2.12. CONCLUSIONS-CLINICAL IMPLICATIONS

The effect of ATM on a common clinical condition - chronic neck pain - will be established based on a standardized procedure with a single blind randomized controlled trial. The acupuncture-stretching combination is used by many researchers and the present study will contribute to the highlight of the effectiveness of this protocol in the examined clinical condition. Finally, a comparison of the two interventions will be carried out in terms of the evaluation parameters (pain sensitivity, cervical ROM, endurance of the deep neck flexor muscles, respiratory function, intensity and quality of pain, functionality and psychological factors).

It should be taken into account that due to the lack of literature the investigation of the effects of FM is an unknown field, while the proper function of the cervical spine is of paramount importance. It attributed to the effects of the neck in spin's function, as well as the function of the upper extremity. Consequently, the ATM technique is a valuable resource in prescribing exercises for patients.

